### 2.6.3 Handling of missing values

As a general rule, missing data will not be imputed in any secondary endpoint analyses.

## **2.6.4      Supportive analyses**

See supportive analyses defined in [Section 2.6.2](#).

## **2.7      Safety analyses**

All safety analyses will be conducted using the SAF. The safety cutoff is defined as 100 days after the last dose administration of study drug (or EOS for participants continue with commercial ofatumumab immediately after EOS, or min(last dose of study medication + 100 days, date of switching to another DMT - 1) for participants who have such switch in the Post-treatment Follow-up period). Unless explicitly otherwise stated, only data up to and including the safety cut-off will be included in the analysis and data beyond this time point for a given subject will be excluded from the safety analysis.

The assessment of safety will be primarily based on the frequency of adverse events (including death and non-fatal serious adverse events). Additional safety assessments include laboratory tests and vital sign measures. Clinically significant findings in these additional safety assessments and other will be reported as adverse events and analyzed as such.

### **2.7.1    Adverse events (AEs)**

An adverse event (AE) is any untoward medical occurrence (i.e., any unfavorable and unintended sign [including abnormal laboratory findings], symptom or disease) in a clinical investigation of a participant after providing written informed consent for participation in the study. That means that a participant can report AEs before having started study medication. For reporting purposes, the main focus will be on treatment emergent adverse event (TEAE), defined as any adverse event which started on or after the day of first dose of study medication or events present prior to the start of treatment but increased in severity based on preferred term.

Except for serious TEAEs and death, only TEAEs up to and including safety cut-off will be included in the analyses. All serious TEAEs and death will be included, regardless of safety cut-off.

AEs will be reported by primary system organ class (SOC) and preferred term (PT) according to the most recent Medical Dictionary for Regulatory Activities (MedDRA). The MedDRA version used for reporting the study will be described in a footnote.

The number and percentage of participants reporting any TEAEs (referred to as incidence of any TEAEs later) will be summarized by primary SOC and PT. Separate summaries (if applicable) will be provided for serious TEAEs, drug related TEAEs, TEAEs leading to permanent discontinuation of study drug, TEAEs causing study drug interruption. Additionally, incidence of any TEAEs will also be summarized by SOC, PT, and maximum CTCAE grade. Missing CTCAE grade will not be imputed.

If a participant reported more than one adverse event within the same primary system organ class, the participant will be counted only once with the maximum CTCAE grade at the system organ class level, where applicable.

All AEs will be presented in listings.

### **2.7.1.1 Adverse events of special interest / grouping of AEs**

Selected tables will be produced for Adverse Events of Special Interest (AESI) (i.e. risks), which will be defined in the electronic case retrieval sheet (eCRS) at the time of analysis implementation (i.e. study database lock). Specifically, incidence of TEAEs that fulfill the risk search terms as defined in eCRS will be summarized, risk name and preferred term. Similarly, separate summaries will be provided for serious TEAEs that fulfill the risk search terms as defined in the eCRS. Additionally, incidence of any TEAEs that fulfill the search terms as defined in the eCRS will also be summarized by risk name, preferred term and maximum severity.

#### **2.7.1.1.1 Injection reaction related AEs**

Incidence of injection site reaction AEs and injection systemic reaction AEs as collected in the relevant CRF pages will be reported as part of the AE summary tables as two preferred terms respectively. For summaries of injection systemic reaction AEs specified in this section, reaction/symptom start date and time will be compared with the injection date and time. Only reactions/symptoms within 24 hours after injections will be included (i.e., time to onset of reaction  $\leq$  24 hours). The time to onset of reaction will be derived as (reaction start date/time – injection date/time) and rounded to the closest integer in hours.

Symptoms listed in the injection site reaction or injection systemic reaction CRF pages will be summarized by providing the number and percentage of participants with each of the symptoms and pre-specified grouping of symptoms as well as overall. These summaries will be provided for each injection up to injection 5 and cumulatively for all injections.

For the injection site reaction, no grouping of symptoms will be specified. For the injection systemic reaction, symptoms will be grouped under 6 categories as defined below and the number and percentage of participants with at least one symptom reported under the category will be provided for each category.

- Skin/mucosal tissue symptoms: Rash, Urticaria, Pruritus general, Flushing
- Respiratory compromise: Dyspnea, Bronchospasm, Chest discomfort, Cough
- Related to change in vital signs: Hypotension, Hypertension, Dizziness, Tachycardia
- Gastrointestinal symptoms: Nausea, Vomiting, Abdominal pain, Diarrhea
- Musculoskeletal/connective tissue symptoms: Arthralgia, Myalgia, Back pain
- Other manifestations: Fever, Headache, Chills, Asthenia, Fatigue, and Other

A table of injection-related reactions reported separately for each injection up to a maximum injection 5 as well as overall for all injections by category of premedication (none, any steroid and non-steroid only) will be provided. A table with incidence rate of Injection-related reactions by maximum CTCAE grade for all injections as well as by injection (up to a maximum of injection 5) will also be given.

## 2.7.2 Deaths

Detailed listing for deaths will also be provided. All deaths as recorded in the final database (i.e. up to the final database lock) will be included.

## 2.7.3 Laboratory data

The summary of laboratory evaluations will be presented for two groups of laboratory tests: Hematology and Chemistry. On presenting summary statistics, laboratory data will be grouped and displayed in an alphabetical order within the Hematology and Chemistry groups.

Descriptive summary statistics (mean, median, standard deviation, Min and Max) of the change from baseline in the laboratory result to each study visit-window will be presented. Change from baseline will only be summarized for participants with both baseline and post baseline values and will be calculated as:

$$\text{change from baseline} = \text{post baseline value} - \text{baseline value}$$

In addition, shift tables will be provided for all parameters to compare a participant's baseline laboratory evaluation relative to the post-baseline values. For the shift tables, the grade level based on CTC grade (as defined by CTCAE as listed in [Section 5.3.3](#)) will be used to evaluate whether a particular laboratory test value was Grade 0, 1, 2, 3, or 4 relative to whether or not the baseline value was Grade 0, 1, 2, 3 or 4. These summaries will be presented by laboratory test.

The number and percentage of participants with new or worsening laboratory abnormalities based on CTC grade (as defined by CTCAE as listed in [Section 5.3.3](#)) in each visit-window and at any time post baseline will be presented. Participants with specific laboratory abnormalities (defined by CTC grade 3 and 4) will be listed.

Number of participants with newly occurring liver enzymes abnormalities will be summarized. Newly occurring liver enzymes abnormalities are defined in [Section 5.3.2](#).

For the shift tables and abnormalities based on CTC grades tables, all applicable post-baseline values will be checked against the respective criteria and the rules for handling multiple laboratory assessments within visit windows will not be applied.

For continuous variables databased as <lower limit, these will be imputed as being half of the lower limit.

All above summaries include only data up to and including safety cut off.

### 2.7.3.1 Other special lab results

Non-routine laboratory data include pregnancy test results, B-cell counts, total IgG and total IgM. All data will be listed appropriately.

The B-cell counts, total IgG and total IgM will be summarized using descriptive statistics by visit-window.

In addition, number and percentage of participants with B-cells < the lower limit of normal (LLN) value (i.e. B-cell depleted) will be presented by visit-window. All B-cell summaries defined in this section will include data up to last dose date + 30.

Number and percentage of participants meeting the notable low level criteria in IgG or IgM at least once will be provided. A notably low IgG level is defined as a level that is 20% below the LLN and a notably low IgM level is defined as a level 10% below the LLN.

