During the Treatment period, all eligible participants will receive initial dosing with ofatumumab 20 mg s.c. injection at Baseline/Week 0 (BL/W0), W1 and W2, followed by subsequent monthly dosing starting at W4 (Month 1/M1; a study month is defined as 28 days). The first s.c. injection at W0 will be administered

All participants will have an End of Study (EOS) visit at the end of the Treatment period, when a participant has reached the maximum of 12-month treatment, or at the time a participant prematurely discontinues study treatment. After study treatment discontinuation, participants may initiate alternative MS therapy according to local standard of care if clinically indicated (refer to [Section 9.3](#)).

[figure not shown]
Post-treatment Follow-up (6 months):

All participants, except for completers who decide to continue with commercially available ofatumumab treatment, will be followed up in the Post-treatment Follow-up period for 6 months after last study drug dose ([Table 8-2](#)). The Post-treatment Follow-up visits should be scheduled relative to the EOS visit and will occur at EOS+3 months and EOS+6 months (End of Post-treatment Follow-up). If a participant prematurely discontinues from Post-treatment Follow-up, the End of Post-treatment Follow-up visit should be arranged as soon as possible. Investigators

may continue to follow participants outside of this study at his/her discretion (for example, if participants have not repleted their B-cells at the end of Post-treatment Follow-up).

Throughout the study periods, participants may have unscheduled visits due to a suspected MS relapse, an acute illness of undetermined cause, for other reasons, or at the discretion of the Investigator (refer to [Section 8.3.1](#)).

Figure 3-1 Study Design

4 Rationale

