6.3.2 Instruction for prescribing and taking study treatment

Ofatumumab will be dispensed starting at W0, and then at scheduled visits throughout the Treatment period according to [Table 8-1](#).

Participants will receive 3 initial s.c. injections of ofatumumab at W0, W1 and W2, followed by subsequent regular monthly dosing starting at W4 (a month is defined as 28 days).

The first s.c. injection at W0 will be administered [REDACTED]

[REDACTED]

[REDACTED]

Participants, who miss s.c. injections or temporarily interrupt study drug without discontinuing from the study or withdrawing consent, will be permitted to resume study drug if determined to be safe and appropriate in the opinion of the Investigator. When resuming study drug, the timing of the next s.c. injection will be determined based on the original study schedule as follows:

- If one monthly injection is missed by more than 1 week, the participant should skip the dose and take the next dose at the time when the next injection would be due according to the original schedule.
- If two or more consecutive monthly injections are missed, the Investigator should inform the local Sponsor Medical Advisor before re-starting dosing.
- If any initial dose (at W0, W1 or W2), or the W4 dose is missed, then the injection should be administered as soon as possible. The next injection should then be administered according to the original schedule.

All dosages prescribed to the participant and all dose administrations and interruptions during the study must be recorded on the eCRF.

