The following informed consents are included in this study:

- Main study consent, which also includes:
 - A subsection that requires a separate signature for the 'Optional Consent for Additional Research' to allow future research on data/samples collected during this study
 - As applicable, Pregnancy Outcomes Reporting Consent for female participants who took study treatment

Women of child bearing potential must be informed that taking the study treatment may involve unknown risks to the fetus if pregnancy were to occur during the study and agree that in order to participate in the study they must adhere to the contraception requirements.

A copy of the approved version of all consent forms must be provided to Novartis after IRB/IEC approval.

Participants might be asked to complete an optional questionnaire to provide feedback on their clinical trial experience.

As per [Section 4.6](#), during a Public Health Emergency as declared by local or regional authorities i.e. pandemic, epidemic or natural disaster, that may challenge the ability to obtain a standard written informed consent due to limits that prevent an on-site visit, Investigator may conduct the informed consent discussion remotely (e.g. telephone, videoconference) if allowable by a local health authority.

Guidance issued by local regulatory bodies on this aspect prevail and must be implemented and appropriately documented (e.g. the presence of an impartial witness, sign/dating separate ICFs by trial participant and person obtaining informed consent etc.).

8 Visit schedule and assessments

The Assessment Schedule ([Table 8-1](#) and [Table 8-2](#)) lists all of the assessments and indicates with "X" or "S" when they are performed. The "X" in the table denotes the assessments to be recorded in the clinical database or received electronically from a vendor. The "S" in the table denotes the assessments that are only in the participant's source documentation and do not need to be recorded in the clinical database. All data obtained from these assessments must be supported in the participant's source documentation.

Participants should be seen for all visits/assessments as outlined in the assessment schedule ([Table 8-1](#) and [Table 8-2](#)) or as close to the designated day/time as possible, with an allowed "injection window" as described in [Section 6.3.2](#). Missed or rescheduled visits should not lead to automatic discontinuation. In the study, one month is defined as 28 calendar days.

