Participants, except for those who will continue with commercially available ofatumumab treatment, will enter the 6-month Post-treatment Follow-up period after EOS as described in [Table 8-2](#).

As per [Section 4.6](#), during a Public Health Emergency as declared by local or regional authorities i.e. pandemic, epidemic or natural disaster that limits or prevents on-site study visits, alternative methods of providing continuing care may be implemented by the investigator as the situation dictates. If allowable by a local health authority and depending on operational capabilities, phone calls, virtual contacts (e.g. tele consult) or visits by site staff/home nursing staff to the participant's home, can replace on-site study visits, for the duration of the disruption until it is safe for the participant to visit the site again.

Table 8-1 Assessment Schedule, Screening and treatment

Period	Screening	Treatment							Treatment	
Visit Name	Screening	BL/W0	W1 (Phone Interview)	W2 (Phone Interview)	W4	M3	M6	M9	M12/EOS	Unscheduled Visit ¹
Days	-30 to -1	-	7	14	28	84	168	252	336	-
Informed consent	X									
Demography, Height	X									
Inclusion / Exclusion criteria	X	X ²								
Medical history/current medical conditions	X									
MS History/Treatments	X									
COVID-19 vaccination status	X	X ³	X	X	X	X	X	X		
Physical Examination	S	S ³			S		S		S	S
Weight, Vital Signs	X	X ⁴			X	X	X	X	X	X
Electrocardiogram (ECG)	X									
Hematology	X ⁵				X	X	X	X	X	
Clinical Chemistry	X ⁵				X	X	X	X	X	
Urinalysis	X ⁵				X		X		X	
Serological markers for hepatitis B ⁶	X ⁵									
HIV antibody screen ⁷	X ⁵									
Syphilis screen ⁷	X ⁵									
Tuberculosis screen ⁷	X ⁵									
Pregnancy and assessments of fertility ⁸	X ⁵	X ³			X	X	X	X	X	
Contraception Status ⁹	X	X ³	X	X	X	X	X	X	X	
MS relapse	X	X ³	X	X	X	X	X	X	X	X
MRI	X					X			X ¹⁰	

Period	Treatment										Treatment
	Screening	BL/W0	W1 (Phone Interview)	W2 (Phone Interview)	W4	M3	M6	M9	M12/EOS	Unscheduled Visit ¹	
Visit Name	Screening										
Days	-30 to -1	-	7	14	28	84	168	252	336	-	
Adverse Events	X	X ³	X	X	X	X	X	X	X	X	
Prior/Concomitant Medications ¹¹	X	X ³	X	X	X	X	X	X	X	X	
Surgical/medical procedures	X	X ³	X	X	X	X	X	X	X	X	
Sample for B-cells ¹²	X	X ³			X	X	X		X		
Sample for IgG and IgM ¹²	X						X		X		
Drug dispensation		S			S	S	S	S			
Drug administration ¹³		X	X	X	Monthly, except for M12/EOS						
Participant diaries ¹⁴					X						
Participant Diary Review					X	X	X	X	X		

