**Table 2-1 General definitions**

Study treatment/Study drug	The investigational drug (ofatumumab) will be referred as study treatment or study drug.
Date of first administration of study drug/first dose date	The first dose date of active study drug (ofatumumab) administration.
Date of last administration of study drug/last dose date	The last dose date of active study drug (ofatumumab) administration.

Study Day 1 or Day 1	The date of first administration of study drug/first dose date.
Study Day	All other study days will be labeled relative to Day 1. For events with dates on or after Day 1, study day for the event is calculated as (event start date – first dose date + 1). For events with dates before Day 1, study day for the event is calculated as (event start date – first dose date).  Day 0 will not be used.
Duration of an event	Duration of an event is calculated as (event end date – event start date +1).
1 month	30 days; to be used in defining 3-month confirmed disability progression.
4 weeks	28 days; to be used in determining target days of scheduled visits. It is based on the scheduled injection frequency for ofatumumab (during the maintenance phase).
Day post-study drug discontinuation	Day post-study drug discontinuation for a particular event is calculated as (event start date – study drug discontinuation date).
Baseline	Baseline is the last assessment with non-missing value obtained prior to the first administration of study drug. No visit windows will be needed for the identification of baseline assessment.  For pulse and blood pressure vital sign values, if 3 measurements were taken on the last visit prior to the first administration of study drug, then the baseline is the average of the non-missing values of them.
On-treatment period	For participants received ofatumumab, on-treatment period includes days from the first injection date until 30 days after the last injection date. The on-treatment definition applies to efficacy analyses and B-cell summaries only.  For calculation of compliance to study drug administration, similar definition of on-treatment period will be used.

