**Table 2-6 Visit-windows for B-cell counts**

Visit-window	Start day	Target Day	End day
Month 1	1	28	56
Month 3	57	84	126

Month 6	127	168	252
Month 12	253	336	420

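### The last dose + 30 day limit on B-cell summaries leaves a two-day margin around the scheduled Month 12 sample, so some completers' Month 12 values will reach listings only

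*SAP*

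**What the plan says.** SAP Section 2.7.3.1 plans descriptive statistics of B-cell counts by visit window. It also plans the number and percentage of participants below LLN, which it treats as depleted. It then limits both: "All B-cell summaries defined in this section will include data up to last dose date + 30". The limit matches the general definitions in SAP Section 2.1.1, where the "on-treatment period includes days from the first injection date until 30 days after the last injection date". The same entry adds: "The on-treatment definition applies to efficacy analyses and B-cell summaries only".

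SAP Table 2-6 assigns B-cell samples to visit windows. Its last two rows (window, start day, target day, end day) read "Month 6 127 168 252 Month 12 253 336 420".

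The protocol fixes the schedule. Section 3 describes three initial injections, "followed by subsequent monthly dosing starting at W4 (Month 1/M1; a study month is defined as 28 days"). Table 8-1 gives drug administration after W4 as "Monthly, except for M12/EOS". It places B-cell samples at Screening, baseline, W4, M3, M6 and M12/EOS, with none at M9.

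On tolerance, Protocol Section 8 asks for visits on schedule "or as close to the designated day/time as possible, with an allowed 'injection window' as described in" Section 6.3.2. The readable part of that section says: "If one monthly injection is missed by more than 1 week, the participant should skip the dose". Other parts of it are redacted.

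**The concern.** The limit falls very close to the day on which the sample is due. Month 12 is the only scheduled check, within the Treatment period, of whether depletion is sustained beyond Month 6. The percentage below LLN at Month 12 is a planned output of a study run to give the Chinese authority data in Chinese patients.

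An EOS visit a few days late is ordinary in a multicentre trial. It would remove a sample that had been scheduled, drawn and analysed. IgG and IgM are taken at the same visit, and the last dose + 30 sentence does not name them, so they are governed by the general safety cut-off. For one slightly late visit, the Month 12 table could therefore hold the participant's immunoglobulins but not the B-cell count.

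Exclusion also depends on the interval from last dose to sample. Participants with a skipped last injection have the longest interval and would always be left out if EOS is on time.

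**Working it through.** **Inputs**

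- Study month: 28 days (Protocol Sections 3 and 8).
- Injections at W0, W1 and W2, then monthly from W4, none at M12/EOS (Protocol Table 8-1).
- EOS for completers at M12 (Protocol Section 8); day 336 in Table 8-1, also the Month 12 target in SAP Table 2-6.
- B-cell summary limit: last dose + 30 days (SAP 2.7.3.1).
- Planned completers: 85 (Protocol 12.8.1).

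**Reproducing the plan's day.** M12 = 12 × 28 = 336, as stated.

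**Planned gap.** The last planned injection is M11 = 11 × 28 = day 308. Gap to EOS = 336 − 308 = 28 days. The limit falls on 308 + 30 = day 338. The gap does not depend on whether the first dose is counted as day 0 or day 1.

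**General rule.** Let L be the days by which the M11 injection is late (negative if early) and D the days by which EOS is late against day 336. The gap is (336 + D) − (308 + L) = 28 + D − L. The sample is kept if this is at most 30, that is, if D − L ≤ 2.

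| M11 injection | First EOS delay excluded |
|---|---|
| on time (L = 0) | 3 days (gap 31) |
| 3 days late | 6 days |
| 7 days late | 10 days |
| 3 days early | 0 days (an on-time EOS has gap 31) |
| skipped (last dose M10, day 280) | 0 days (336 − 280 = 56) |

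**Other routes into a summary.** SAP 2.7.5 applies no safety cut-off and covers B-cell repletion, but includes only participants who stop treatment prematurely. The first post-treatment B-cell sample is due at EOS + 3 months, day 336 + 84 = 420, which is 420 − 308 = 112 days after the last dose, so the limit excludes it too. An unscheduled sample between day 253 and last dose + 30 could fill the Month 12 window, because safety analyses map unscheduled visits, but none is planned. Otherwise the late value appears only in listings.

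**Size.** The readable text gives no EOS window in days and no distribution of delays. The shares below are illustrations. They count whole days, equally likely and independent, and a sample is lost when D − L > 2.

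| Assumed EOS timing | Assumed M11 timing | Share lost | Of 85 |
|---|---|---|---|
| ±3 days | 0–7 days late | 1/56 = 1.8% | 1.5 |
| ±5 days | 0–7 days late | 6/88 = 6.8% | 5.8 |
| ±7 days | 0–7 days late | 15/120 = 12.5% | 10.6 |
| ±3 days | on time | 1/7 = 14.3% | 12.1 |
| 0–7 days late | 0–7 days late | 15/64 = 23.4% | 19.9 |
| ±5 days | on time | 3/11 = 27.3% | 23.2 |
| ±7 days | on time | 5/15 = 33.3% | 28.3 |
| 0–7 days late | on time | 5/8 = 62.5% | 53.1 |

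Anyone who skipped the M11 injection comes on top of these.

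**The case against.** The best defence is that the limit is deliberate. SAP 2.1.1 defines an on-treatment period ending 30 days after the last injection and applies it expressly to B-cell summaries; 2.7.3.1 carries that out. Table 2-6 only labels a sample with a visit, while the on-treatment rule decides whether it enters. The two can operate together, so a reader who infers that the SAP contradicts itself would be wrong. A participant 56 days past the last dose is outside the on-treatment question by design. All of this stands, and it is why the on-treatment summary should be kept.

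A reader might also infer that the Month 12 percentage is biased toward depletion. The documents do not support this as a finding. They give no repletion time, and Protocol Section 3 allows that some participants may still not have repleted at the end of the six-month follow-up. Nothing shows that a sample at 31 to 37 days, or even 56 days, would change the percentage below LLN.

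It is also fair to say that late M11 injections offset late EOS visits, that excluded values are still listed, and that B-cell count is not named among the endpoints in Protocol Table 2-1. With no hypothesis testing, no inference depends on it.

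What remains is practical: a limit two days beyond the scheduled sample will discard planned data for ordinary visit delays, and no other summary picks them up for completers.

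**Conclusion.** The point holds as a minor one. The planned interval from last dose to the Month 12 B-cell sample is 28 days against a limit of 30. With M11 on schedule, an EOS visit three or more days late leaves the Month 12 summary and the percentage below LLN. The threshold shifts day for day with the M11 injection date, and a skipped M11 injection excludes an on-time EOS sample outright.

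The size is not known. The illustrations run from about 2% to over 60% of completers, and the loss would be nil if every participant fell within the margin. No narrower range is defensible, since Section 6.3.2 is partly redacted and its readable one-week figure concerns injections, not EOS visits. The direction of any bias is plausible, mainly for skipped M11 injections, but not shown.

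Only a descriptive safety and biomarker summary is affected. The primary and MRI endpoints are not.

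**What to change.** In SAP 2.7.3.1:

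- Keep the last dose + 30 summary and label it as the on-treatment result.
- Add a Month 12 summary (descriptive statistics and percentage below LLN) using the scheduled M12/EOS sample of every participant who completes the Treatment period, under the Table 2-6 window and taken before any new DMT or commercial ofatumumab. Naming the M12/EOS sample prevents a follow-up sample near day 420 from standing in for it.
- Footnote how many of these samples were taken more than 30 days after the last dose, separating participants with a skipped M11 injection.

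The cost is a short SAP addition, one extra summary row and a footnote. Data collection does not change. The downside is that the added row includes some values well beyond 30 days after the last dose, up to about 56 days where M11 was skipped. That is why it should sit beside the on-treatment result and not replace it.
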